## Post-op Telehealth Mindfulness Protocol for Spinal Surgery

proposed research will address this gap by establishing the feasibility and acceptability of an optimized mindfulness-based intervention (MBI), delivered using a telehealth approach (to maximize accessibility), for improving pain-related outcomes and opioid use.

**MBIs have a well-established evidence base as efficacious interventions for reducing chronic pain symptoms.** Well-controlled studies indicate that MBIs are efficacious for improving physical functioning and pain interference, and reducing commonly co-occurring symptoms such as depression and anxiety in chronic pain populations. Furthermore, in RCTs targeting individuals taking opioid medications for chronic pain, MBIs were effective at reducing opioid misuse, craving, and/or opioid use. MBIs are now recommended as first-line nonpharmacological treatment for chronic low back pain. The most extensively studied MBIs (e.g. mindfulness-based stress reduction and mindfulness-based cognitive therapy), demonstrate similar efficacy as traditional cognitive behavioral therapy for chronic low back pain. However, pilot research with chronic low back pain patients suggests that different patient characteristics predict better response to one type of treatment over another, lending support for research and dissemination of multiple psychosocial treatment options to which patients can be individually matched.

Central to MBIs is systematic and intensive training in mindfulness meditation practices. Mindfulness skills involve the self-regulation of attention to present-moment experience and the development of non-judgmental awareness of moment-by-moment experience, including thoughts, emotions, or sensations that arise, even if unpleasant or unwanted. Mindfulness meditation engages emotional, cognitive, and sensory networks in the brain that regulate pain, with meditators showing heightened sensory processing coupled with attenuated cognitive and emotional evaluation of pain sensations. Patients with chronic low back pain who participated in an MBI reported reduced pain catastrophizing and increased pain acceptance and self-efficacy to manage pain. Studies in low back pain patients and healthy participants demonstrated that after mindfulness training, participants experienced lowered pain sensitivity to thermal or electrical stimuli. There are no prior studies that have tested an MBI early following spine surgery as a means to prevent or mitigate poor post-surgical outcomes.

**Barriers to accessing MBIs impact successful implementation after spine surgery.** The standard MBIs are typically located at major medical centers and offered as in-person, group-based interventions with 8 weekly sessions lasting 2 to 2 ½ hours each. This format is highly impractical for post-surgical spine patients, many of whom live hours away from surgical centers. Furthermore, group-based MBIs are frequently offered only a few times per year, and thus may not be available to patients early after surgery, a time when patients have indicated a need for additional nonpharmacological intervention to help optimize recovery. Telehealth is increasingly used in healthcare systems to reach patients across long distances who would not otherwise access healthcare services or research opportunities, and thus is a promising platform for reaching post-surgical patients. The proposed study will leverage existing telehealth technology to study a telehealth MBI (delivered live via online video platform) in both one-on-one and group formats and tailored specifically to address the needs of patients following spine surgery. The result will be a clinically significant advance in the care of the large population of patients undergoing spine surgery each year.

## INNOVATION

**The proposed study is innovative in its tailoring of an existing MBI specifically for use in the orthopaedic surgery population.** MBIs have been used for the management of chronic pain, but

## Post-op Telehealth Mindfulness Protocol for Spinal Surgery

patients may experience distinct concerns after orthopaedic surgery. For example, severe, acute post-operative pain due to surgical tissue damage can occur concurrently with residual chronic pain, and at times lead to new chronic pain. Patients report experiencing post-operative distress, fear and avoidance of movement, and unmet expectations. In addition, patients may desire to taper off of pain medications as quickly as possible after surgery. Data from this study will help optimize an MBI for patients undergoing spine surgery, with application to other orthopaedic surgery populations.

**The proposed study is also innovative in its use of telehealth technology**, which enables broad reach of the intervention to patients regardless of distance or transportation access and costs. Additional flexibility and opportunity to individually tailor the intervention is offered by the one-on-one, rather than group-based format. Telehealth delivery allows for the integration of a biopsychosocial approach into routine post-surgical spine care, as is recommended, without introducing substantial burden on patients. Other preliminary work by the principal investigator suggests that providing an MBI over telehealth is feasible in a chronic pain population, but has yet to be investigated in post-surgical spine patients.

[figure not shown]
**Finally, the project is innovative in its integrated use of both quantitative and qualitative methods to produce an optimized MBI that is both feasible and acceptable in this population.**

## Post-op Telehealth Mindfulness Protocol for Spinal Surgery

### 3. Study Design

**3.1. Design Overview.** The study will use a two-arm, nonrandomized mixed-methods design to: 1) evaluate the feasibility and acceptability of a one-on-one telehealth MBI delivered via live, online video in approximately 24 patients following elective lumbar spine surgery for degenerative spine conditions, and 2) adapt the telehealth MBI to the specific concerns of post-surgical patients using both qualitative and quantitative data from post-intervention surveys and semi-structured interviews. Participants will be enrolled in either the individual intervention or the group intervention, and enrollment for each intervention will occur sequentially. Patient-reported outcomes (pain-related and psychosocial variables) and self-reported and electronically verified opioid use will be collected at pre-surgery, 2-weeks post-surgery (pre-intervention), and 3 months post-surgery (post-intervention). Semi-structured interviews will be conducted at post-intervention

**Figure 1. Study Design**

**3.2 Telehealth Mindfulness Intervention.** The telehealth MBI consists of 8, weekly sessions with a study interventionist. The one-on-one intervention sessions will each be 75 minutes long, with the exception of the first session, which will be 90 minutes long. The group interventions sessions will each be 90 minutes long. Participants will be asked to complete the 8 sessions within 10 weeks to allow for missed weeks. All sessions will be conducted using an IRB-approved HIPAA compliant telehealth platform in which the intervention is delivered via secure internet video link and audio-recorded for fidelity monitoring. The intervention is based on an existing manualized MBI (mindfulness-based cognitive therapy for chronic pain). Mindfulness-based cognitive therapy was originally developed for preventing relapse of depression and has since been adapted and tested in chronic pain populations, including chronic low back pain and headache pain. The intervention, typically delivered in-person in a group setting, will be formatted for both one-on-one and group telehealth delivery, with subsequent data-driven adaptation planned. Participants who do not have their own device with microphone and video camera (e.g. computer, tablet, or smart phone) will be given a tablet to use during the study.

At the core of the telehealth MBI is systematic instruction and practice in mindfulness meditation, which trains the self-regulation of attention to present moment experience and fosters a nonjudgmental and accepting response to one's experience, including pain sensations. Participants learn meditation practices that can be completed sitting or lying down as well as gentle mindful movement practices that can be completed while walking, standing, or sitting. Education on the brain-pain relationship (gate-control and neuromatrix theory) is also provided and mindfulness skills are discussed within the context of pain management. Because of the importance of cognition and emotion in pain processing, the intervention incorporates elements of cognitive therapy including exercises in recognizing the connection between thoughts, emotions, behaviors, and stress as they relate to chronic pain. Participants learn to become aware of the mental events and behavioral responses that amplify pain

## Post-op Telehealth Mindfulness Protocol for Spinal Surgery

interference and distress, and to process and respond to unpleasant sensations and emotions more skillfully. Each session focuses on didactic information (introduced interactively), practicing a new mindfulness skill with discussion, reviewing previous skills, and assigning home practices. Participants will be requested to keep track of their practicing by completing a Home Record Practice. The participants will be giving a paper copy and then asked to complete in a Survey electronically each week.

**Interventionist Training and Fidelity Monitoring.** The PI will oversee intervention training and delivery with [name] (co-investigator). Our study interventionist will be a doctoral trained clinical psychologist who has completed prior training in mindfulness skills facilitation and cognitive therapy through graduate-level work and/or formal training workshop(s). The PI will provide structured training in the study intervention manual with a 1-day workshop covering intervention content. This workshop will cover each session module, with role-playing interactions. There will be weekly supervision of the study interventionist by the PI, through the review and discussion of audio-recorded sessions and fidelity checklists. All sessions of the first 2 patients will be monitored and reviewed and then 25% of the sessions will be randomly selected for review during weekly sessions. The interventionist will complete a checklist of all the components delivered during each session and make note of any protocol deviations.

**Potential adverse effects:** Based on results of previous literature, we expect there to be no more than minimal risk in this study; however, literature on mindfulness-based interventions have not systematically included adverse event reporting, although most studies have not reported any serious risk from participating. There have been reports of increased emotional distress and increased awareness of both positive and negative experiences, which may initially increase distress when participants are not used to directing attention towards unpleasant thoughts, feelings, and sensations. There is the potential for increased negative emotions at the beginning of the course, as well as the possibility that history of trauma, abuse, or substance addiction could heighten negative emotional reactions. With a trained interventionist, reactions can be managed and appropriate referrals made. There also the possibility of emotional distress related to completing questionnaires about mood and pain-beliefs.

### 4. Patient Selection.

**4.1. Overview and Clinical Centers.** Approximately 34 patients scheduled to undergo lumbar spine surgery will be recruited from Vanderbilt University Medical Center. The Vanderbilt Comprehensive Spine center treats large numbers of lumbar degenerative conditions and has a proven track record for prospective study of patients having lumbar spine surgery. Eligible patients will be identified and recruited at the participating clinical center subject to the inclusion and exclusion criteria listed below.

#### **Inclusion criteria:**

- 1) English-speaking adults
- 2) Between the ages of 18 and 90
- 3) Scheduled for a laminectomy and/or fusion
- 4) scheduled for their first lumbar spine surgery

## Post-op Telehealth Mindfulness Protocol for Spinal Surgery

- 5) Radiographic evidence of a degenerative condition including but not limited to *spinal stenosis, spondylosis with or without myelopathy, and spondylolisthesis*
- 6) Presence of back and/or lower extremity pain persisting for at least 3 months
- 7) Access to stable internet.
- 8) Able to participate in weekly, remote sessions with a study therapist for 8 weeks after surgery

### **Exclusion criteria:**

- 1) Microsurgical technique as the primary procedure (i.e. isolated laminotomy or microdiscectomy)
- 2) Having surgery for the primary indication of a spinal deformity
- 3) Having surgery secondary to pseudarthrosis, trauma, infection, or tumor
- 4) Current/history of a primary psychotic or major thought disorder or hospitalization for reasons related to psychosis
- 5) Diagnosis of Alzheimer's disease or another form of dementia
- 6) Traumatic Brain Injury (greater than mild severity)
- 7) History of bipolar disorder or dissociative disorder
- 8) Schizophrenia or other psychotic disorder (e.g. brief psychotic disorder, delusional disorder)
- 9) Active substance use disorder (in past month)
- 10) Current Posttraumatic Stress Disorder (PTSD) symptoms (in past month)

## **5. Trial Protocol**

**5.1. Overview.** The patient-related activities of the postoperative telehealth mindfulness trial can be divided into the following phases.

- Phase 1: Consent into study and screening for eligibility
- Phase 2: Enrollment into trial prior to surgery, preoperative data collection
- Phase 3: Postoperative Baseline data collection (2 weeks after surgery)
- Phase 4: Intervention (8 weeks)
- Phase 5: Post-intervention data collection and semi-structured interviews (3 months after surgery)

**5.2. Phase 1: Consent into Study and Screening for Eligibility.** Patients will be approached for their consent to participate in the study following their preoperative clinic visit either at the clinic as available or over the phone, with the permission of the treating surgeon. If over the phone, participants will sign an e-consent form through a REDCap survey link. The study coordinator will perform the consent process using a scripted dialogue and materials developed for the study.

Patients will then be screened for eligibility in the surgical center or over the phone by the research coordinator. Screening through the medical record will occur prior to surgery and a scheduled preoperative clinic visit. Additional screening will occur either immediately after the preoperative clinic visit at the Spine Center or after the visit over the phone by the study coordinator through a list of screening questions. All potentially eligible patients will be entered into REDCap, a study number assigned, and eligibility criteria confirmed.

## Post-op Telehealth Mindfulness Protocol for Spinal Surgery

**5.3. Phase 2: Enrollment and Preoperative Data Collection.** Once consented into the study and determined to be eligible, patients will complete a preoperative questionnaire using a REDCap survey either at the clinic after the visit, online after the visit, or over the phone after the visit if preferred. This self-report assessment will gather data on patient demographic and injury characteristics, medical and social history, pain self-efficacy, negative affect, dispositional mindfulness, concerns about pain, current opioid use and preoperative levels of pain and disability. Opioid prescription and dosages will also be extracted from the electronic medical record.

**5.4. Phase 3: Baseline Data Collection (2 weeks after surgery).** Study participants who complete surgery will be emailed or texted (based on participant preference) a REDCap survey to collect baseline data at two-weeks after surgery. They can also complete the survey at the postoperative clinic visit or over the phone. Similar to the pre-operative questionnaire, this self-report assessment will gather data on pain self-efficacy, negative affect, dispositional mindfulness, concerns about pain, current opioid use and levels of pain and disability. Opioid prescription and dosages will also be extracted from the electronic medical record.

At this time, participants will also meet with the research coordinator, either at their post-operative clinic visit or by phone, to become oriented to the telehealth platform that will be used during intervention sessions. If the participant does not have their own device for use during the intervention, they will be provided with a tablet by the research coordinator.

**5.5 Phase 4: Treatment.** Once the patient has been consented, undergone surgery for a lumbar degenerative condition, and completed the baseline assessment, the participant will begin the telehealth mindfulness intervention. The interventionist will call the participant to schedule the first treatment session. For participants enrolled in a group, the coordinator will gather participants' availability and schedule the group sessions at a time when the interventionist and as many participants as possible are available. Patients will complete 8, weekly sessions over telehealth (audio and video), and will have 10 weeks to complete the intervention to allow for 1 to 2 possible missed weeks. Participants will be asked to complete a paper form asking about their daily practice of what they have learned and then enter that information weekly into the Home Practice Record Survey electronically.

**5.6. Phase 5: Post-Treatment Data Collection (3-months after surgery).** After completing the intervention (3 months after surgery), participants will be emailed or texted a REDCap survey. They can also complete the survey at the postoperative clinic visit or over the phone. Similar to the pre-operative and post-operative baseline questionnaire, this self-report assessment will gather data on pain self-efficacy, negative affect, dispositional mindfulness, pain sensitivity, current opioid use and levels of pain and disability. It will also gather data on participant satisfaction with the telehealth mindfulness intervention. Opioid prescription and dosages will also be extracted from the electronic medical record.

The research coordinator will assist patients with scheduling a post-treatment qualitative phone interview, which will be conducted by a study investigator with qualitative research experience. Each phone interview will last approximately 30 minutes and be audio-recorded. The semi-structured interview guide consists of open-ended questions and probes focusing on obtaining participant

## Post-op Telehealth Mindfulness Protocol for Spinal Surgery

experiences and perceptions of the telehealth delivery format, intervention components (mindfulness skills, didactics, home practice), perceived benefits, relevance to post-surgical concerns, concerns not addressed by the intervention, barriers to participation, and suggestions to improve the intervention. The interview guide is designed to revised as needed throughout the study (e.g. changes in wording of questions and probes to be more clear; addition of questions that seem pertinent based on prior participants' responses to interview questions).

### 5.7. Primary and Secondary Outcomes

#### ***Primary outcomes:***

Intervention feasibility and acceptability (enrollment, session attendance, homework completion, intervention retention, intervention satisfaction, semi-structured interview).

#### ***Secondary Outcomes:***

- 1) PROMIS-29 – Pain Intensity and Pain Interference
- 2) Pain Bothersomeness (1 item)
- 3) Oswestry Disability Index (ODI)
- 4) Self-reported and EMR-collected opioid dosage
- 5) PROMIS-29 – Depression scale
- 6) PROMIS-29 – Anxiety scale
- 7) Pain Self-efficacy questionnaire (PSEQ)
- 8) Five-Facet Mindfulness Questionnaire-15 (FFMQ-15)
- 9) Perceived Stress Scale – 4
- 10) Pain Catastrophizing Scale (PCS)
- 11) Tampa Scale for Kinesiophobia - 13

### 5.8 Safety Issues.

**5.8.1. Safety Concerns Related to the Therapeutic Treatment.** We anticipate based on previous research of mindfulness training interventions that the study will pose minimal safety risk; most studies have not reported any serious risk from participating in structured MBIs. There have been reports of increased emotional distress and increased awareness of both positive and negative experiences, which may initially increase distress when participants are not used to directing attention towards unpleasant thoughts, feelings, and sensations. With a trained instructor, reactions can be managed. It is possible that history of trauma or substance addiction could heighten negative emotional reactions. Participants with unstable psychiatric illness or substance addiction will be excluded from participation. There may also be distress related to answering questionnaires about mood and pain beliefs.

**5.8.2. Safety Issues Related to Patient Privacy.** Patients will only be identified by an identification code and not by their name, SSN, or hospital medical record number. Study personnel will maintain a separate confidential enrollment log which matches identifying codes with the patients' names and addresses (available only to study personnel). Enrollment logs will be kept in a secured, password-protected file on a VUMC-approved server. All study material will be maintained in strict confidence.

## Post-op Telehealth Mindfulness Protocol for Spinal Surgery

For participants enrolled in the group intervention, there is a risk to loss of confidentiality by nature of being in a group with other patients. All participants will be asked to agree to keep other participants' information confidential within the group setting.

**5.9 Retention.** The study participants will receive an honorarium in recognition of their time and effort. Participants will be compensated \$20 each for completing the preop intake assessment survey, the 2-week postop baseline assessment survey, and the 3-month postop assessment and intervention assessment survey (up to \$60) and \$25 for completing the semi-structured phone interview, for a possible total of \$85 per participant. Participants will not be compensated for completing the weekly Home Practice Record Survey. We will keep participants engaged through reminder emails and phone calls for intervention sessions and assessments.

**5.10. Management of Concomitant Conditions.** Concomitant conditions will be managed with the standards of care at the local treatment facility and should not be affected by study participation.

**5.11. Adverse Event Reporting.** We will monitor and report adverse events to ensure patient safety.

**5.11.1. Definitions.** We will use the following definitions in identifying adverse events.

- **Adverse event.** An adverse event is any untoward medical occurrence that may present itself during treatment or administration with clinical procedure and which may or may not have a causal relationship with the treatment. Adverse events include any unanticipated problems involving risks to participants, or breaches of protocol which might entail risk to participants. The term "unanticipated problem" includes both new risks and increased rates of anticipated problems.
- **Serious adverse event.** A serious adverse event (SAE) is an adverse event occurring at any time during the study that results in death, inpatient hospitalization or prolongation of existing hospitalization, or a persistent or significant disability/incapacity. Other events may also be considered an SAE if, based on medical judgment, the event jeopardized the patient to the point of requiring medical or surgical intervention to prevent the occurrence of any of the conditions for an SAE listed above.
- **Unexpected adverse event.** An unexpected adverse event is any adverse event with specificity or severity that is not consistent with the risk information in the study protocol.
- **Associated with the use of the treatment** means that there is a reasonable possibility that the adverse experience may have been caused by the treatment.

**5.11.2. Monitoring and Reporting Adverse Events.** Adverse events will be recorded on study data forms whether or not they are thought to be associated with the study or with one of the study treatments. Adverse events may be discovered during regularly scheduled visits or through unscheduled patient contacts between visits. IRB requirements for reporting adverse events will be followed. Where applicable, signs and symptoms associated with the adverse event will be graded as to severity by the clinical study staff as mild, moderate, or severe using the Common Terminology Criteria for Adverse Events.

**5.11.3. Reporting Serious Adverse Events.** Serious adverse events (SAE) must be reported upon discovery. This will involve completing an SAE case report form describing the severity and details of the event. IRB requirements for reporting SAEs will be followed.

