## 6. Statistical Analyses.

**6.1. Statistical Analysis Plan.** Descriptive statistics will be used to summarize quantitative feasibility outcomes with numbers and rates. Benchmarks for success of the telehealth MBI will be: 1) enrollment rate of at least 50% of eligible patients; 2) 90% of sessions attended on average; 3) 80% of home practice completed on average; 4) intervention retention of at least 90%; 5) moderate to high intervention satisfaction rated by at least 80% of participants.

Transcription of interview data will be verified prior to analysis. The PI and study personnel will conduct line by line analysis using Dedoose analytic software. Themes and textual examples will be independently identified and subsequently discussed for consensus. Analysis will be an ongoing, iterative process following each 2 to 4 interviews to ensure that data saturation ultimately occurs before discontinuing interviews. A codebook will be generated by isolating individual quotes and refined as additional interviews are coded. Thematic analysis of codes will be used to identify emergent themes, or patterns of meaning, found in the data with regards to participant experiences with the telehealth MBI and specific post-surgical concerns. Quantitative and qualitative data results will be merged to identify aspects of the telehealth MBI that need to be adapted to optimize acceptability for post-surgical patients.

Within-group, within-subject changes from baseline to the follow-up post-intervention assessment in pain-related outcomes, opioid use, and psychosocial characteristics will be explored by examining change in scores and their respective standard errors with 95% confidence intervals.

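### No instrument described in the protocol asks participants about harms, so early non-serious distress may be under-recorded by an unknown amount and a low adverse-event count could not be read as good tolerability

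*Combined protocol and SAP*

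**What the plan says.** Section 5.11.2 states where harms might come to light: "Adverse events may be discovered during regularly scheduled visits or through unscheduled patient contacts between visits". It also sets a recording rule: "Adverse events will be recorded on study data forms whether or not they are thought to be associated with the study". The rest of 5.11 covers grading and reporting. Section 5.11.1 defines the term broadly but in medical language: "An adverse event is any untoward medical occurrence that may present itself during treatment or administration with clinical procedure". Distress is not named there.

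Under Potential adverse effects in Section 3.2, the protocol remarks that "literature on mindfulness-based interventions have not systematically included adverse event reporting". It then says what it foresees and when: "There is the potential for increased negative emotions at the beginning of the course".

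Section 6.1 opens with "Descriptive statistics will be used to summarize quantitative feasibility outcomes with numbers and rates". It goes on to the five feasibility benchmarks, the interview analysis and change from baseline in the secondary outcomes. Adverse events do not appear there, nor among the outcomes in Section 5.7.

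**The concern.** The protocol identifies a weakness of earlier mindfulness studies and names the harm it considers most plausible. It then describes a way of finding events that depends on someone noticing or mentioning them. The recording rule does not help with this, because it applies only to events already found.

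Whether patients in the first weeks after spine surgery tolerate the programme is part of its acceptability, and acceptability is a primary outcome. The study's product is an adapted intervention. If transient distress goes unrecorded, those adapting it may conclude that the opening sessions are well tolerated when the question was never put.

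Section 5.11.1 also counts an increased rate of an anticipated problem as an unanticipated problem. That is hard to judge when occurrence is not asked about in the same way for everyone.

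**Working it through.** The plan states no adverse-event rate, safety threshold or safety precision, so there is no figure to reproduce. The check has two parts.

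**1. Where could a question about harms be asked?**

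| Contact or instrument | Section | Content described | Question on harms? |
|---|---|---|---|
| Pre-surgery, 2-week and 3-month surveys | 3.1, 5.3, 5.4, 5.6 | Pain, disability, opioid use, mood and beliefs; satisfaction at 3 months | None described |
| Eight weekly sessions | 3.2, 5.5 | Teaching, practice, discussion, home assignments | None described |
| Interventionist's session checklist | 3.2 | Components delivered, protocol deviations | None described |
| Audio review | 3.2 | All sessions of the first 2 patients, then a random 25%, for supervision and fidelity | Not its stated purpose |
| Home practice record (weekly, electronic) | 5.5 | Daily practice | None described |
| Exit interview | 5.6 | Experience, benefits, relevance, unaddressed concerns, barriers, suggestions | No harms topic listed |
| Review of accumulating data | Synopsis, Safety monitoring | Data already collected | Sees only what was captured |

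On timing, the 2-week survey comes before the intervention and the next survey is at 3 months. The eight sessions may take up to 10 weeks, so the whole course lies between two outcome assessments (2 + 10 = 12 weeks). The distress scales (PROMIS depression and anxiety, Perceived Stress Scale) are analysed as change from baseline to the post-intervention assessment. That can miss distress that arose early and settled, or worsening in a few individuals.

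**2. What could a count of zero mean?**

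Inputs: about 24 completers, 16 individual and 8 group (synopsis). The share s of affected participants who are detected is not given anywhere. It is an assumption, shown from 25% to 100%.

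The exact two-sided 95% (Clopper-Pearson) upper limit for zero events in n is U = 1 − 0.025^(1/n).

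- n = 24: 1 − 0.025^(1/24) = 14.2%
- n = 16: 1 − 0.025^(1/16) = 20.6%
- n = 8: 1 − 0.025^(1/8) = 36.9%

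These limits assume full capture and reflect sample size alone. With a detection share s, the recorded rate is s times the true rate, so the limit on the true rate is U/s. For 0/24:

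| Assumed share detected | U/s | Upper limit on true rate |
|---|---|---|
| 100% | 14.2/1.00 | about 14% |
| 75% | 14.2/0.75 | about 19% |
| 50% | 14.2/0.50 | about 28% |
| 25% | 14.2/0.25 | about 57% |

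The same point can be made with an assumed true risk of 10% and n = 24. The chance of recording no event is (1 − 0.10·s)^24. This is 0.90^24 = 8% at full capture, 0.95^24 = 29% at one half and 0.975^24 = 55% at one quarter.

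**The case against.** The best defence is that the study has far more contact with participants than its adverse-event paragraph suggests. Section 3.2 states that "The telehealth MBI consists of 8, weekly sessions with a study interventionist". Section 7.2 says the interventionists are psychologists trained to respond to increased distress, severe depression and suicidal ideation, with the PI and the surgeon notified. The PI supervises weekly from recordings, distress scales are collected, and the exit interview is open-ended. Section 7.4 promises immediate reporting. The data forms and the SAE form are not in the documents and may contain a prompt. The plan is also a feasibility pilot with no safety endpoint.

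Much of this stands. A reader might infer that harms are found only by chance. The documents do not support that: these contacts make capture better than chance, particularly for serious events. A reader might also infer that group participants could disclose distress only in front of others, or that capture must differ by format. That is conjecture. Each participant also has an individual survey and phone interview, and reminder calls are planned (Section 5.9). Nor does the plan say it will conclude safety from a zero count.

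The defence does not supply the missing step. Each safeguard responds to distress that is noticed, or measures something else, and none is described as asking every participant about harms. Since the forms cannot be seen, the claim is limited to what the protocol specifies.

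**Conclusion.** The point holds as a gap in ascertainment and reporting, and it should be corrected. As described, the plan may under-record non-serious early distress by an amount that cannot be estimated, in the period where the protocol itself places the risk. A low or zero count would then not be evidence of good tolerability.

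The size depends on an unknown detection share. Over the assumed range of 100% down to 25%, the upper limit compatible with 0/24 runs from about 14% to 57%. No single value in that range is supported by the documents.

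It would be wrong to attribute the 14.2%, 20.6% and 36.9% limits to the passive method. They would remain with perfect capture, and better asking cannot narrow them. Asking removes much of the uncertainty about detection, not the imprecision of a small pilot. With no untreated control group, events also cannot be separated from ordinary post-surgical recovery.

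**What to change.** - **Ask.** Add one standard item on new or worsened distress or other problems to the weekly electronic Home Practice Record Survey and to the 3-month survey. The 2-week survey precedes the intervention, so the item there would give only a baseline. State in 5.11.2 that these answers are a source of adverse events.
- **Review and follow up.** Have the existing coordinator review the answers. Section 5.9 says the weekly survey is unpaid, and participants who disengage may not return it, so follow up non-responders through the reminder contacts already planned.
- **Report.** In 6.1, give the number and proportion of participants with any event, any treatment-associated event and any SAE. Report overall and by format, among everyone who starts the intervention and not only completers, with exact 95% confidence intervals.
- **State the limits.** Say that precision stays wide even with full capture (upper limits of 14.2% for 0/24, 20.6% for 0/16 and 36.9% for 0/8), and that without a control group events cannot be separated from normal recovery.

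The cost is one item in surveys already sent, one table and some coordinator time. More unrelated post-surgical complaints will be recorded and need classifying, and association with treatment remains a judgement. No extra visits are needed.
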